5.5 Subject Disposition

Enrolled

Individuals are considered enrolled when they have met Part 1 and Part 2 eligibility criteria. Enrolled individuals are referred as “subjects”.

Randomized

Individuals are considered randomized if they have been assigned a randomization number. Randomized individuals are referred to as “subjects”.

Completing the DBTP

Subjects are defined as completing the DBTP if they complete the week 12 assessment. It will be derived from the End of Double-blind Treatment Phase eCRF with “Completed” as the reason for ending study phase.

Completing Study

Subjects are defined as completing study if they complete the whole 28 weeks of study evaluation. It will be derived from the End of Study eCRF page with “Completed” as the primary reason for ending study.

Exposed to IP

Subjects are defined as exposed if they receive at least one dose of IP.

Completing the Double-Blind IP

Subjects are defined as completing double-blind IP if they complete **week 10** IP dose. **It will be derived from the End of Investigational Product Administration eCRF page with “Completed” as the reason for ending IP.**

On-study

Subjects are considered on-study if they have been randomized and have not yet had their end of study visit.

5.6 Arithmetic Calculations

Duration of Migraine

The number of years from the diagnosis date (DXDT) of migraine (migraine with aura or migraine without aura, whichever is earlier) to the date informed consent is signed.

If month or day of the diagnosis date is missing, follow the formula below to calculate the duration:

Observed portion	Missing portion	Formula to Calculate Duration
Year, Month, Day		(Informed Consent Day – DXDT)/365.25
Year, Month	Day	[Year(Informed Consent Day)-Year(DXDT)]+ [Month(Informed Consent Day)-Month(DXDT)]/12 if it equals 0, add 1 month or 1/12 years (this is to avoid a disease duration of 0)
Year	Month, Day	[Year(Informed Consent Day)-Year(DXDT)] if it equals 0, add 1 month or 1/12 years (this is to avoid a disease duration of 0)

Exposure

For all calculations of exposure, dose date refers to receiving dose > 0, but can include partial dose.

Age at Onset of Migraine

Age at enrollment – [date at enrollment in years-DXDT of migraine in years (migraine with aura or migraine without aura)]

Duration of DB IP Exposure

Duration = Minimum (Last DB Dose Date + 27, EOS Date) – First DB Dose Date + 1

Change from Baseline in Monthly Efficacy Measurement

The change from baseline in monthly efficacy measurement is the monthly efficacy measurement in the monthly interval prior to the given time point minus the baseline monthly efficacy measurement. Please refer to the Monthly Interval for Efficacy Endpoints defined in [Section 5.4](#). For example, change from baseline in monthly migraine days for Week 12 will be calculated based on the following:

(Monthly migraine days during the week 12 interval) – (monthly migraine days during the baseline phase)

If the baseline or post-baseline value is missing, then the change from baseline is set to missing.

The following efficacy endpoints will be calculated as above:

- Change from baseline in monthly migraine days
- Change from baseline in monthly acute migraine-specific medication treatment days

- Change from baseline in monthly physical impairment domain score as measured by the MPFID
- Change from baseline in monthly impact on everyday activities scores as measured by the MPFID
- Change from baseline in monthly headache (migraine and non-migraine headache) days
- Change from baseline in monthly average severity of migraine pain
- Change from baseline in monthly acute headache medication treatment days
- Change from baseline in monthly mean overall impact on everyday activities as measured by the MPFID stand-alone item
- Change from baseline in monthly days with impact on everyday activities as measured by the MPFID domain
- Change from baseline in monthly days with physical impairment as measured by the MPFID domain
- Change from baseline in the Cranial Autonomic Parasympathetic Symptom (CAPS) scale total score
- Change from baseline in monthly migraine-related disability and productivity as measured by MMIDAS
- Change from baseline in daily activity impact of headache as measured by HIT-6
- Change from baseline in the first 4 weeks in monthly migraine days

Change from Baseline in Mean Monthly Efficacy Measurement over Multiple Months

- The Change from Baseline in Mean Monthly Efficacy Measurement is the Arithmetic mean of monthly values for the months considered - baseline monthly value

Percent Change from Baseline

The change from baseline divided by baseline and multiplied by 100:

$$(\text{Post-baseline} - \text{Baseline}) * 100 / \text{Baseline}$$

If the baseline value is 0 and the post-baseline value is also 0, then the percent change from baseline is set to 0. If the baseline value is 0 and the post-baseline value is non-zero, then the percent change from baseline is set to be missing

Percent change from baseline in (mean) monthly migraine days which is used to determine 50%, 75%, and 100% responder will be calculated as above.

Subject Incidence

The subject incidence for a given event in a given period is defined as the number of subjects with at least one reported occurrence of the event divided by the number of

subjects who entered that period. For subjects with multiple occurrences of the same event, the event will only be counted once per subject.

Medication Overuse at baseline

Medication overuse at baseline will be considered if any of the following criteria are present:

- **≥ 15 days of simple analgesic,**
- **≥ 10 days of triptans,**
- **≥ 10 days of ergotamines,**
- **≥ 10 days of combination therapy intake of any combination of ergotamines, triptans, opiates, combination-analgesic medication (includes the case of more than 1 medication category within one visit).**

Medication Overuse during the DBTP

Medication overuse will be considered present if any of the following criteria are met during a **single** month of the DBTP: ≥ 15 days of simple analgesics; ≥ 10 days of triptans; ≥ 10 days of ergotamines; ≥ 10 days of combination therapy intake of any combination of ergotamines, triptans, opiates, **combination-analgesic medications**.

5.7 Disease Characteristics

Migraine-Specific Medications

Migraine-specific medications include two categories of medications: triptan-based and ergotamine-based migraine medications collected from the subject's eDiary.

Treatment Failure of Migraine Prophylactic Medications

Treatment failure of prior migraine prophylactic medications is determined by “Reason for stopping” as “Intolerance” or “Lack of efficacy” in the Migraine Prophylactic Medication eCRF page.

Response Status to AMG 334

At least a 50% reduction from baseline in monthly migraine days at month 3 for subjects who received consecutive 3 doses of AMG334 since the first dose of AMG334.

6. Analysis Sets

6.1 Full Analysis Set

The Full Analysis Set (FAS) consists of all subjects who were randomized in the study. The FAS will be used to tabulate subject disposition, demographic data, baseline disease characteristics, and important protocol deviations for all randomized subjects.

6.2 Primary Analysis Set

The Primary Analysis Set (PAS) (ie, Efficacy Analysis Set) will be used to carry out the primary analyses of the efficacy endpoints. **It consists of all subjects who were randomized**, received at least 1 dose of investigational product, and have at least 1 postbaseline monthly eDiary measurement. Subjects will be analyzed according to their randomized treatment group, regardless of treatment received. The PAS will be used to analyze all efficacy and PRO endpoints.

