2.1 Objectives and Endpoints

Objectives	Endpoints
Primary	

To evaluate the effect of AMG 301 compared to placebo on the change from the baseline period in monthly migraine days in subjects with migraine	
Change from the baseline period in monthly migraine days. The monthly migraine days will be calculated using the migraine days over the last 4 weeks of the 12-week double-blind treatment period
The primary estimand consists of: 
The target population, which is patients with chronic or episodic migraine who have failed at least one prophylactic treatment for migraineThe variable, which is the change in monthly migraine days from the baseline period over the last 4 weeks of the 12-week double-blind treatment periodThe population-level summary measure, which is the difference in the mean of the variable between each AMG 301 treatment group and the placebo groupThe intercurrent event, adherence to treatment will be ignored and the primary endpoint will be assessed for all subjects who receive at least 1 dose of investigation product and have at least 1 postbaseline monthly eDiary measurement regardless of adherence to treatment	
The primary estimand is the difference in means between each AMG 301 treatment group and placebo in the change in monthly migraine days from the baseline period over the last 4 weeks of the 12-week double-blind treatment period for patients with chronic or episodic migraine who have failed at least one prophylactic treatment for migraine who are randomised, receive at least one dose of investigation product and have at least 1 post baseline monthly eDiary measurement.	
Secondary	

To evaluate the effect of AMG 301 compared to placebo on the proportion of subjects with at least 50% reduction from the baseline period in monthly migraine days	
Achievement of at least a 50% reduction from the baseline period in monthly migraine days in the last 4 weeks of the 12-week double-blind treatment period

To evaluate the effect of AMG 301 compared to placebo on the change from the baseline period in monthly acute migraine-specific medication treatment days	
Change from the baseline period in monthly acute migraine-specific medication days in the last 4 weeks of the 12-week double-blind treatment period.

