
To evaluate the effect of AMG 301 compared to placebo on the change from the baseline period in monthly physical impairment domain score as measured by the Migraine Physical Function Impact Diary (MPFID)	
Change from the baseline period in physical impairment domain scores as measured by the MPFID over the last 4 weeks of the 12-week double-blind treatment period

Objectives	Endpoints

To evaluate the effect of AMG 301 compared to placebo on the change from the baseline period in monthly impact on everyday activities domain score as measured by the MPFID	
Change from the baseline period in impact on everyday activities domain scores as measured by the MPFID over the last 4 weeks of the 12-week double-blind treatment period.

To evaluate the safety and tolerability of AMG 301	
Incidence of treatment-emergent adverse eventsChange from baseline in clinical laboratory values and vital signs

The secondary estimands for each of the secondary objectives except the last one are similar to the primary estimand but differ in the following ways:

- The variables are the endpoints listed above for each secondary objective
- The population-level summary measure for the first secondary objective is the difference in proportions of subjects who achieve at least a 50% reduction in monthly migraine days between each AMG 301 group and the placebo group

The estimands for the last secondary objective is similar to the primary estimand but differ in the following ways:

[figure not shown]
- The variables are the incidence of adverse events and change from baseline in clinical laboratory values and vital signs during the 12-week double-blind treatment period
- The population-level summary measures for the incidence of adverse events is the count of adverse events during the 12-week double-blind treatment period and the difference in means for the change from baseline variables for each AMG 301 treatment group and the placebo group
- The intercurrent event, adherence to treatment will be ignored and the secondary endpoint will be assessed for all subjects in the target population**

CCI

CCI

CCI

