Monthly frequency measurements (including migraine days, headache days, migraine attacks, acute headache medication treatment days, acute migraine-specific medication treatment days)	If diary days in entire baseline or interval post baseline ≥ 14 (including retrospective eDiary days), then do proration; Else monthly measurement is set to missing [A diary day is a day with all headache related questions completed retrospectively or not]	Number of observed migraine days * 28/ Number of information days in interval [information day is a diary day or headache day]
Monthly average of severity of migraine pain (1-3 scale)	If diary days in entire baseline or interval post baseline ≥ 14 (including retrospective eDiary days), then calculate the average; Else missing	Arithmetic mean of the observed pain scores of qualified migraine headaches over the monthly interval
Monthly average of MPFID domain scores	If days with observed daily domain score in interval ≥ 14 then calculate the average; Else missing	Arithmetic mean of the observed daily domain score over the monthly interval
Monthly impairment day for Everyday Activity and Physical Impairment domains and overall	If days with observed daily domain score in interval ≥ 14 then do the proration; Else missing	Number of observed impairment days * 28/ Number of days with domain score in monthly interval

Completely missing COAs and subject-completed assessments (eg, HIT-6, MIDAS) scheduled to be collected at office visit at certain assessment will not be imputed.

Missing safety endpoints and antibody data will not be imputed, except for adverse event dates as described in [Section 8.3](#).

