8.3.3 Missing Post-baseline Evaluation in the DBTP

Primary analysis of continuous efficacy endpoints during the 12-week randomized DBTP will be conducted using the generalized linear mixed model on observed data without subject-level imputation.

In sensitivity analyses of primary and secondary efficacy endpoints during the 12-week DBTP, missing continuous monthly efficacy endpoints will be handled using multiple imputation (MI) with the assumption of missing not at random (MNAR) (with control-based pattern imputation). The continuous monthly efficacy endpoints will be computed as the mean over the last four weeks of the DBTP based on the observed and imputed values.

In the non-responder imputation (NRI) method, post-baseline missing dichotomous efficacy endpoints (**responder [Yes/No] based on $\geq 50\%$, $\geq 75\%$ and 100% reduction from baseline in monthly migraine days**) during the DBTP will be imputed as

non-responder at each corresponding time point. The dichotomous endpoints derived based on the mean change from baseline over the last 4 weeks of the DBTP will be imputed as non-responder if the mean change from baseline over the last 4 weeks of the DBTP is missing.

If the proportion of missing data for the primary endpoint is high (eg, > 20%), further analyses will be performed to

- examine the frequency and reason of missing data
- determine if there are any patterns in the missing data
- distinguish true missing values from other unknown values (eg, due to measurement or sample processing error)

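### The non-responder and control-based imputation analyses run on a set that requires a post-baseline diary month, so dosed subjects with no evaluable month are never imputed

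*SAP*

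**What the plan says.** **Analysis set.** SAP 6.2 requires that a PAS subject was randomised, "received at least 1 dose of investigational product, and have at least 1 postbaseline monthly eDiary measurement". It then says: "The PAS will be used to analyze all efficacy and PRO endpoints". Protocol 10.2.1.2 carries the same diary condition. The Full Analysis Set has no efficacy role in SAP 6.1: "The FAS will be used to tabulate subject disposition, demographic data, baseline disease characteristics, and important protocol deviations for all randomized subjects".

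**When a monthly value exists.** Table 8-1 (SAP 8.3) prorates a monthly frequency only if the interval holds at least 14 diary days, retrospective entries included. Below that, "Else monthly measurement is set to missing". In Table 5-1 (SAP 5.4) the first post-baseline interval starts on Study Day 1. If the week 4 dose was not given, it ends at Study Day 28 or end of study, whichever is earlier.

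**Missing data.** SAP 8.3 lists early withdrawal among the causes of missing data. Its sensitivity analyses are non-responder imputation for categorical endpoints and control-based multiple imputation under MNAR for continuous ones. SAP 8.3.3 sets a missing response to "non-responder at each corresponding time point".

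**Estimand.** In SAP 2.1 the target-population bullet has no diary condition. The intercurrent-event bullet and the closing sentence add one; the latter covers patients "who are randomised, receive at least one dose of investigation product and have at least 1 post baseline monthly eDiary measurement". The efficacy secondaries inherit it: "The secondary estimands for each of the secondary objectives except the last one are similar to the primary estimand". The safety estimand is assessed in all subjects in the target population.

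**The concern.** Having an evaluable diary month is an outcome observed after randomisation. A sensitivity analysis for missing data should cover the subjects whose data are missing, and the earliest losses have the least information of all. The PAS removes exactly those subjects before either imputation method is applied.

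The estimand has the same gap. SAP 2.1 ignores adherence to treatment, which is a treatment-policy position, and in the same bullet conditions on a post-randomisation measurement. At stake is how far the imputation analyses can support the main result, and possibly the main responder comparison itself, depending on which statement in SAP 9.5 governs.

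**Working it through.** There is no planned figure to reproduce: the sample size text is redacted in both documents, and no dropout rate is visible. The check is therefore a reading of the rules followed by an illustration on assumed rates.

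**1. Who is left out.**
- A subject dosed on Study Day 1 who leaves on day 10 has at most 10 diary days in the first interval. Since 10 < 14, the week 4 value is missing. There are no later intervals, so the subject is outside the PAS.
- A subject who stays on study but stops the diary for good before 14 entries has no value in any interval, and is also outside.
- A subject who lapses in month 1 but completes at least 14 diary days in a later interval is in the PAS and can be imputed.
- A subject who stops drug but stays on study is asked by Protocol 7.4.3.1 to keep completing the diary, and so can enter the PAS.

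**2. Which analyses are touched.**
- Mixed model on observed data: a subject with no post-baseline value contributes nothing whether in the set or not. No effect.
- Non-responder imputation and control-based imputation: both would assign such a subject an outcome, but only if the subject is in the set. Affected.
- Main responder analysis: the table opening SAP 9.5 and SAP 10 specify a CMH test on observed data. The paragraph before Table 9-1 specifies CMH after imputing missing data as non-response. If that paragraph governs, the main responder analysis is affected too.

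**3. Illustration, non-responder imputation.** Let e be the share of dosed subjects in an arm who are outside the PAS. Counting them as non-responders multiplies the PAS rate by (1 − e):

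difference = 0.40 × (1 − e_active) − 0.30 × (1 − e_placebo)

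The 40%, 30% and all values of e are assumptions.

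| e_active | e_placebo | Calculation | Difference (points) |
|---|---|---|---|
| 0% | 0% | 0.400 − 0.300 | 10.0 |
| 2% | 2% | 0.392 − 0.294 | 9.8 |
| 5% | 2% | 0.380 − 0.294 | 8.6 |
| 8% | 3% | 0.368 − 0.291 | 7.7 |
| 2% | 5% | 0.392 − 0.285 | 10.7 |

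**4. Illustration, control-based imputation.** If excluded active subjects take the placebo mean, the difference becomes about δ × (1 − e_active). For an assumed δ of 1.5 days this gives 1.47 days at 2%, 1.425 at 5% and 1.35 at 10%.

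**5. Scale.** With 335 randomised 4:3:3, the arms are about 134 placebo and 100 per dose. The standard error of 40% v 30% is √(0.40 × 0.60/100 + 0.30 × 0.70/134) = √0.00397, or 6.3 points. The shifts in step 3 (0.2, 1.4, 2.3 and 0.7 points) are about 0.03, 0.2, 0.4 and 0.1 standard errors.

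**The case against.** The strongest reply is that few subjects will be affected. Randomisation requires at least 80% diary compliance at baseline, subjects who stop drug are followed, and exclusion needs fewer than 14 diary days in every post-baseline interval. The set is prespecified with the same diary condition in protocol and SAP, the primary test does not depend on it, and this is a phase 2a trial. SAP 9.2 tabulates withdrawals and reasons by arm, so a marked imbalance would be seen. SAP 8.3.3 adds an examination of missing-data patterns if the missing proportion is high (for example, above 20%). All of this stands, and it limits the likely size.

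A reader might infer that the restriction favours AMG 301, with six injections per visit driving early losses on active drug. The documents do not support that. Protocol 7.1.1 gives every arm, placebo included, six injections at each dosing visit, and nothing visible predicts more early loss on active. Placebo subjects might equally leave early, and the last row of the table shows the difference then rising.

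A proposal to use all dosed subjects can also be criticised because dosing itself follows randomisation. That is fair in principle. Under blinding, with randomisation and first dose planned for the same day, it is a much weaker condition than a diary month. Using all randomised subjects avoids the question.

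The reply does not answer the main point. Disposition tables show that subjects were lost, but they do not put those subjects into the imputation analyses, and no wider set is named for them.

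**Conclusion.** The gap is real and worth correcting. The SAP does not name a set for each sensitivity analysis line by line; the restriction follows from the general PAS statements in SAP 6.2 and 8.3, and nothing contradicts it.

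Its effect depends on how many dosed subjects have no evaluable month and how unevenly they fall across arms, and neither can be derived from the documents. On the assumed rates above, the responder difference moves from 10 points to between 7.7 and 10.7. That is modest against the sampling error, and the direction is open. The primary mixed-model result is not in question.

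**What to change.** - Keep the PAS for the observed-data mixed model.
- Run every non-responder-imputation and control-based multiple-imputation analysis on all randomised subjects who received at least one dose, or on all randomised subjects. For those with no post-baseline month, impute from the baseline value and strata. SAP 8.3.2 relies on the baseline diary-compliance criterion for baseline values to exist, and that criterion applies to every subject eligible for randomisation.
- In SAP 2.1, delete the diary condition from the intercurrent-event bullet and the closing estimand sentence, so that both match the target-population bullet.
- In SAP 9.5, state once whether the main CMH test uses observed data or non-responder imputation. If the latter, use the wider set there too.
- Report the number excluded from the PAS by arm, with reasons.

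The cost is SAP wording, minor programming and slightly lower responder rates. No new data are needed.

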6.3 Safety Analysis Set

The Safety Analysis Set (SAS) consists of all enrolled subjects who received at least 1 dose of investigational product. Subjects will be analyzed according to the randomized treatment unless a subject has received the incorrect dose during the entire DBTP period. Where a subject has received the incorrect dose during the entire DBTP, the subject will be analyzed according to treatment received. Analyses for safety endpoints and summary of investigational product administration will use this analysis set.

